3.1.2 Open-Label Extension

Once subjects reach Week 48, they will have the option to roll over into the OLE, with all subjects receiving 15 mg PO losmapimod tablets BID. Subjects who wish to roll over into the OLE must complete all procedures from the Week 48 end of placebo-controlled treatment period/start of OLE visit ([Table 13-1](#)).

Subjects will remain in the OLE until study drug approval or until the study is discontinued by the sponsor. All subjects who complete or discontinue from treatment will complete a safety follow-up visit 7 days (± 3 days) after the last dose of study drug.

During the OLE, subjects will attend clinic visits approximately every 12 weeks ([Table 13-2](#)). Study drug (open-label losmapimod) will be administered BID and should be taken with food.

Blood samples for PK (losmapimod concentration) will be collected after dosing at each clinic visit, preferably ≥ 1 hour after dosing. Serum and plasma samples will be collected twice a year (ie, every 24 weeks [Week 72, Week 96, Week 120, Week 144, Week 168, etc.]) and will be used to aid in the discovery of potential biomarkers of FSHD disease activity and treatment effects.

Musculoskeletal MRIs will be performed twice a year (ie, every 24 weeks [Week 72, Week 96, Week 120, Week 144, Week 168, etc.]) Safety and tolerability will be evaluated based on the assessment of AEs, AESIs, SAEs, laboratory tests, ECGs, vital signs, and physical examinations.

The full schedule of assessments for the OLE is provided in [Table 13-2](#). Scheduled visits may be split over 2 days if required, with a maximum of 5 business days in between visits. Unscheduled visits may be performed if clinically indicated. Subjects can travel for MRI if needed, but the use of a study-approved MRI scanner should be consistent during the trial.

Fulcrum Therapeutics

Losmapimod

Protocol FIS-002-2019, Version 4.0 (COVID-19 Pandemic Emergency Amendment)

10 April 2020

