4.2.2 Handling of Withdrawals

Subjects are free to withdraw from the study or study treatment at any time upon request. Subject participation in the study may be stopped at any time at the discretion of the investigator or at the request of the sponsor.

Subjects who discontinue study treatment or active participation in the study will no longer receive study drug. When a subject withdraws from the study treatment or active participation in the study, the reason(s) for withdrawal shall be recorded by the investigator on the relevant page of the electronic case report form (eCRF).

If a subject prematurely discontinues study treatment, they will be encouraged to remain in the study and continue with all other aspects of the study. If appropriate, subjects can restart study drug at the 7.5 mg PO BID dose at the investigator's discretion (depending on the reason for discontinuation of study treatment), after approval from the sponsor.

If a subject decides to prematurely discontinue study treatment and not continue with all other aspects of the study, they will be considered to have withdrawn from the study. If a subject withdraws from the study, they will be asked to complete the early termination (ET) visit as soon as possible after the decision to terminate study participation and to complete the safety follow-up visit 7 (± 3) days after their last dose of study drug. If the ET visit will be scheduled more than 7 days after the last dose of study drug, the safety follow-up and ET visits may be combined, with no duplication of assessments required.

Subjects who fail to return for final assessments will be contacted by the site in an attempt to have them comply with the protocol. In the case of subjects being lost to follow-up, at least 3 documented attempts to contact the subject must be made.

Fulcrum Therapeutics Losmapimod
Protocol FIS-002-2019, Version 4.0 (COVID-19 Pandemic Emergency Amendment) 10 April 2020
It is vital to obtain follow-up data on any subject withdrawn because of an AE or SAE. In every case, efforts must be made to undertake protocol-specified, safety, follow-up procedures.

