7.4 Analysis Sets

The following analysis sets will be used in the statistical analyses.

Full analysis set (FAS): The FAS will consist of all subjects who are randomly assigned to receive double-blind study drug in the placebo-controlled treatment period. All analyses using the FAS will group subjects according to randomized treatment. The FAS is the main analysis population for key study endpoints ([Section 7.6.1](#)). For the secondary and exploratory endpoints, subjects who already transitioned into the OLE portion under protocol version 3.0 will be analyzed as randomized, in this analysis population.

Per-protocol set (PPS): The PPS will consist of all FAS subjects who fulfill all inclusion/exclusion criteria and do not have any significant protocol deviations. All analyses using the PPS will group subjects according to randomized treatment. PPS analyses will be conducted for key study endpoints ([Section 7.6.1](#)) to assess robustness of key study inferences.

Safety analysis set: The safety analysis set will consist of all subjects who receive any study drug. All analyses using the safety analysis set will group subjects according to treatment actually received.

Pharmacokinetic analysis set: The PK analysis set will consist of all subjects who receive at least 1 dose of losmapimod and have evaluable PK data for losmapimod.

Pharmacodynamic analysis set: The PD analysis set will consist of all subjects who receive at least 1 dose of losmapimod and have evaluable PD data for losmapimod.

Open-label losmapimod (Pre-COVID-19) analysis set: This analysis set will consist of subjects who were already transitioned into open-label losmapimod under version 3.0 of the protocol. This analysis set will be used for sensitivity analysis, to assess secondary/exploratory endpoints in this subset of subjects.

Fulcrum Therapeutics

Losmapimod

Protocol FIS-002-2019, Version 4.0 (COVID-19 Pandemic Emergency Amendment)

10 April 2020

Open-label analysis set: The open-label analysis set will consist of all subjects who complete 24 weeks of treatment in the placebo-controlled treatment period and receive at least 1 dose of open-label losmapimod in the OLE. Safety and efficacy analyses in the OLE will be based on this analysis set.

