7.6.6 Safety Analyses

Safety data in the placebo-controlled treatment period will be analyzed using the safety analysis set and summarized by treatment group and visit (if applicable) using descriptive statistics. Safety data in the OLE will be analyzed using the open-label analysis set.

Treatment-emergent AEs will be summarized by MedDRA system organ class and preferred term; separate summaries will be produced for treatment-related AEs, AESIs, SAEs, and discontinuations due to AEs. Laboratory tests, vital signs, findings from physical examinations, and ECGs will be summarized for changes over time during treatment using descriptive statistics.

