8.2.1. Sensitivity Analyses of Primary Endpoint

Missing Data: The following sensitivity analyses will be conducted on the primary efficacy endpoint to assess the impact of missing data on study conclusions:

- **Last Observation Carried Forward (LOCF):** Post-baseline missing DUX4 score will be imputed using baseline DUX4 score for each subject with missing data. Patients who are missing the baseline assessment will be excluded from the analysis.
- **Placebo Mean Imputation:** Post-baseline missing DUX4 score will be imputed using mean post-baseline score calculated from the placebo arm. Patients who are missing the baseline assessment will be excluded from the analysis.
- **Observed worst case imputation:** For subjects with missing baseline DUX4, imputation will be done using the smallest baseline DUX4 score among subjects with non-missing data. For subjects missing post-baseline DUX4, imputation will be done using the highest DUX4 score among subjects with non-missing data.

DUX4 by timepoint: The primary endpoint will be analyzed separately for Week 16 and Week 36 to assess the impact of biopsy timing on study conclusions.

COVID-19 related treatment disruptions: Subjects may be diagnosed with COVID-19 and proceed on a quarantine or have no access to study treatment for a prolonged duration. These subjects will be excluded from analysis of the primary endpoint, to assess the impact of COVID-19 related treatment disruptions on the study conclusions.

Excluding cross-over subjects: Subjects who already transitioned into open label losmapimod based on the prior protocol version will be excluded from the analysis.

DUX4 change excluding subjects with censored laboratory observations at baseline:
Subjects with censored observations at baseline for any of the transcripts in the panel of 6 DUX4-regulated transcripts will be excluded from the analysis.

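### The open-label analysis set requires 24 weeks of placebo-controlled-period treatment but OLE entry does not, so a treated subject could be left out of the OLE safety summaries

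*Protocol*

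**What the plan says.** Protocol 7.4 sets two joint conditions for the open-label analysis set: "all subjects who complete 24 weeks of treatment in the placebo-controlled treatment period and receive at least 1 dose of open-label losmapimod in the OLE". It then gives the set's use: "Safety and efficacy analyses in the OLE will be based on this analysis set". Protocol 7.6.6 repeats this for safety: "Safety data in the OLE will be analyzed using the open-label analysis set". The same section assigns the safety analysis set, which has no minimum duration, to the placebo-controlled period.

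Entry to the extension is worded differently. Protocol 3.1.2 says "Once subjects reach Week 48, they will have the option to roll over into the OLE", and that those who wish to do so "must complete all procedures from the Week 48 end of placebo-controlled treatment period/start of OLE visit". It states no minimum time on drug.

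Protocol 4.2.2 covers subjects who stop study drug: "they will be encouraged to remain in the study and continue with all other aspects of the study". That section also makes two statements about later dosing. One says that subjects who stop get no further study drug. The other says "If appropriate, subjects can restart study drug", subject to the investigator's discretion and the sponsor's approval.

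SAP 8.2.1 foresees that some subjects may "have no access to study treatment for a prolonged duration" because of COVID-19. SAP Section 1 leaves the OLE to a separate SAP, which is not among the documents.

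**The concern.** Long-term safety and tolerability is the OLE's primary objective (Protocol 2.2.1), so this set carries the OLE's main analysis. A safety population would normally include everyone exposed in the period, as the placebo-controlled safety set does. Here membership also depends on treatment history before the period began, and the entry rule has no matching condition. Someone can therefore be exposed in the OLE yet fall outside the set. If those left out include subjects who stopped early for tolerability, the OLE event rates would describe a more selected group than the one treated.

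**Working it through.** The plan gives no figure on this point to reproduce. The check compares the texts and then bounds the number affected.

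**1. Entry against membership.** Entry (Protocol 3.1.2): reach Week 48 and complete its procedures. Membership (7.4): 24 weeks of treatment completed, plus one open-label dose. The second condition of membership follows from being treated in the OLE. The first is not implied by entry.

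**2. Is there another set for the gap?** The safety analysis set is assigned to the placebo-controlled period (7.6.6). The Open-label Losmapimod (Pre-COVID-19) set has its own safety tables in SAP 15.8, but it holds only subjects who moved to open label under version 3.0. Neither covers a Week 48 entrant with under 24 weeks of treatment.

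**3. What does completing 24 weeks of treatment mean?** The documents do not define it. Three readings are possible for a subject who reaches Week 48:

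- Calendar time in the period: everyone who reaches Week 48 passes, and the condition has no effect.
- Total time on drug: with g weeks off drug, time on drug is 48 − g, and the subject fails when 48 − g < 24, that is g > 24. This applies equally to a supply gap and to a stop followed by a restart.
- An unbroken 24 weeks from Day 1: any interruption that begins before Week 24 fails.

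A discontinuer who stopped for good at week s < 24 fails under the last two readings, but matters only if admitted to the OLE. A subject who stopped for good between Weeks 24 and 48 meets the condition.

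The visit window adds a smaller ambiguity. Week 24 is Day 168 (24 × 7; SAP Table 4-1) with a window of ±5 days (Protocol Table 13-1), so a visit on Day 163 is in window. A strict 168-day count could exclude a subject who rolled over at such a visit.

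**4. How many?** Of 80 enrolled, 12 had rolled over at Week 24 (Protocol 3.1.1) and are largely unaffected, which leaves 80 − 12 = 68. The documents give neither the share p who stop before 24 weeks of treatment nor the share q of those who then take open-label drug. Both are assumed here. Number excluded = 68 × p × q:

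| p | q = 25% | q = 50% | q = 100% |
|---|---|---|---|
| 0% | 0 | 0 | 0 |
| 5% | 0.85 | 1.70 | 3.40 |
| 10% | 1.70 | 3.40 | 6.80 |
| 15% | 2.55 | 5.10 | 10.20 |

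The range is 0 to about 10. At p of 5% to 10% with q of 50% it is about 2 to 3.

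**The case against.** The strongest reply is that 4.2.2 says subjects who discontinue treatment get no more study drug. The only way back that it describes is a restart needing approval, and that restart is at a dose other than the OLE dose in 3.1.2. No passage says that a discontinuer may enter the OLE. SAP 3.1 describes those awaiting the Week 48 rollover as still on randomized treatment. On this view few or none of those treated in the OLE could fail the 24-week condition. This stands to the extent that OLE entry by a permanent discontinuer is neither granted nor barred consistently. It does not remove the restart route or the supply-gap route, and 3.1.2 does not carry the 4.2.2 sentence over as an entry rule.

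The 24-week figure also has a possible purpose: it admits both the 12 Week 24 rollovers and the Week 48 entrants, whereas a 48-week condition would lose the 12. That is fair, and the figure is not shown to be an oversight. But one open-label dose already admits both groups.

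The supply-gap route is narrow. If time on drug is what counts, it takes more than 24 of 48 weeks off drug, and courier supply (Protocol 5.2, 5.4) is meant to limit gaps. The SAP 8.2.1 text concerns a sensitivity analysis of DUX4, not the OLE. It shows only that long gaps were foreseen.

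A reader might go further and infer that serious events in excluded subjects would appear in no OLE table. The documents do not support that. The OLE SAP is not supplied and could define the set differently. All data are to be listed (Protocol 7.6), serious events are reported within 24 hours (6.2.1.6), and the safety review committee sees safety data for all subjects (11.1.1). The issue is who is counted in the summaries, not whether events reach oversight.

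**Conclusion.** The mismatch is real: as written, the set named for OLE safety can exclude a subject who takes open-label losmapimod. Its reach is limited. The number affected is unknown, probably small and possibly zero. The range of 0 to about 10 rests wholly on assumed stopping and entry rates, and on a reading of the 24-week condition that is not mere calendar time.

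A reader might infer that the rule will make OLE event rates look too low. That direction is plausible, because those left out may have stopped for adverse events, but it is not established. Allocation was 1:1, so for about half the subjects completing 24 blinded weeks shows tolerance of placebo, not of losmapimod. A contrast such as 3/76 (3.9%) reported as 0/73 would need every event to fall in the excluded subjects. It would also use 76, the planned number randomized, as an OLE count that no document gives.

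The change is still worth making, because the set carries the OLE's primary objective and the condition serves no stated purpose for safety.

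**What to change.** In Protocol 7.4 and the OLE SAP, define the OLE safety set as every subject who receives at least one open-label losmapimod dose, with no condition on earlier treatment duration. If a 24-week condition is wanted, keep it only for a descriptive subgroup or a sensitivity set, and state there whether it means calendar time, total time on drug or unbroken treatment, and how interruptions and restarts count.

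Separately, the sponsor should reconcile the two statements in Protocol 4.2.2 on study drug after discontinuation with each other and with OLE entry and dosing in 3.1.2. No clinical rule is proposed here.

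The cost of the definition change is one sentence in each document, with no new data or procedures. It can be made before any OLE analysis.

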7.5 Description of Subgroups to Be Analyzed

Any planned subgroup analyses will be described in the SAP(s).

7.6 Statistical Analysis Methodology

Continuous variables will be summarized using the mean, standard deviation, median, minimum, and maximum. Categorical variables will be summarized using frequency counts and percentages. Data will be listed in data listings.

Details of the statistical analyses, methods, and data conventions are described in the SAP(s).

All statistical tests will be 2-sided and performed using a 0.05 significance level.

Details of multiplicity adjustment, if any, will be fully described in the SAP(s).

7.6.1 Hypothesis Testing on Key Study Endpoints

Hypothesis testing on key study endpoints will be conducted using the FAS.

A sequential testing procedure will be used to control for Type I Error to test the following key study endpoints:

- DUX4 change from baseline (Week 16 or Week 36)
- LMV change from baseline (Week 48)
- FSHD TUG (Week 48)

The testing hierarchy will be provided in the SAP. Each endpoint will be tested at approximately 5% alpha in a hierarchical manner, using the final test-alpha obtained from O'Brien-Fleming Spending Function ([Section 7.6.8](#)).

Fulcrum Therapeutics

Losmapimod

Protocol FIS-002-2019, Version 4.0 (COVID-19 Pandemic Emergency Amendment)

10 April 2020

7.6.2 Analysis of Primary Endpoints

The primary endpoint of the placebo-controlled treatment period is the change from baseline in DUX4 activity in affected skeletal muscle at Week 16 or Week 36, as measured by QRT-PCR in a panel of DUX4-regulated gene transcripts. An analysis of covariance (ANCOVA) model will be used to analyze the change from baseline in DUX4 activity in affected skeletal muscle, with repeat number category and treatment group as fixed effects and baseline DUX4 activity in affected skeletal muscle as a covariate. Least-square (LS) mean, standard error, and 95% CI of the LS mean will be provided for each treatment group. The difference in LS means between treatment groups and the 95% CI of the difference will also be calculated. The final p-value will be compared against the significance level of approximately 0.05 ([Section 7.6.8](#)). All available data will be used. Details will be provided in the SAP(s).

The FAS will be used for the primary analysis for the placebo-controlled treatment period.

The analysis for the primary endpoint for the OLE is described in [Section 7.6.6](#).

7.6.3 Analysis of Secondary Endpoints

Secondary endpoints (detailed in [Section 7.1.2](#) and [Section 7.2.2](#)) will be summarized using descriptive statistics.

Continuous endpoints with multiple post-baseline assessments will be analyzed using mixed-effect model for repeated measures (MMRM) methods including repeat number category, treatment group, visit, and treatment-by-visit interaction as fixed effects and baseline value as a covariate. Continuous endpoints with a single post-baseline assessment will be analyzed using ANCOVA methods, with repeat number category and treatment group as fixed effects and baseline value as a covariate. Secondary endpoints in the OLE will be summarized according to the treatment assigned at randomization. For all subjects, changes in measurements will be calculated relative to measurements obtained at baseline (ie, prior to first dose in the placebo-controlled treatment period).

Further details of these endpoints are presented in [Section 7.6.5](#), [Section 7.6.6](#), and the SAP(s).

Fulcrum Therapeutics

Losmapimod

Protocol FIS-002-2019, Version 4.0 (COVID-19 Pandemic Emergency Amendment)

10 April 2020

7.6.4 Analyses of Exploratory Endpoints

Exploratory endpoints (detailed in [Section 7.1.3](#) and [Section 7.2.3](#)) will be summarized using descriptive statistics. Confidence intervals will be included as appropriate. When appropriate, continuous exploratory endpoints will also be analyzed using ANCOVA or MMRM methods similar to those used for the primary and secondary endpoints. Any treatment group comparisons will be in the nature of hypothesis generation, and any statistical inference will not have any confirmatory value. Exploratory endpoints in the OLE will be summarized according to the treatment assigned at randomization.

7.6.5 Pharmacokinetic and Pharmacodynamic Analyses

Plasma PK concentrations at each time point for losmapimod will be presented in listings and summarized in tables. Losmapimod concentrations in skeletal muscle biopsy at each time point will also be presented in listings and summarized in tables. The summary tables will display the following descriptive statistics: n, mean, standard deviation, coefficient of variation, median, minimum, and maximum.

The individual and mean plasma concentrations and the individual and mean concentrations in skeletal muscle biopsies will be presented by collection time in figures on linear scales.

The target engagement estimates of losmapimod in peripheral blood and skeletal muscle biopsies will be presented in listings and summarized in tables. The summary tables will display the following descriptive statistics: n, mean, standard deviation, coefficient of variation, median, minimum, and maximum. Within-group LS means, the associated standard errors and 2-sided 95% CIs, treatment differences in LS means and the associated 2-sided 95% CIs, and 2-sided p-values will be derived from the ANCOVA model and presented in the tables.

Population PK and PK/PD models may be developed to address program objectives that require an integrative interpretation of these study results. These may include investigations of the nature of the PK/PD relationship and the use of these study results as part of a larger model-based data analysis. If population PK and PK/PD analyses are performed, those results will be reported separately from the results of this study.

Fulcrum Therapeutics

Losmapimod

Protocol FIS-002-2019, Version 4.0 (COVID-19 Pandemic Emergency Amendment)

10 April 2020

7.6.6 Safety Analyses

Safety data in the placebo-controlled treatment period will be analyzed using the safety analysis set and summarized by treatment group and visit (if applicable) using descriptive statistics. Safety data in the OLE will be analyzed using the open-label analysis set.

Treatment-emergent AEs will be summarized by MedDRA system organ class and preferred term; separate summaries will be produced for treatment-related AEs, AESIs, SAEs, and discontinuations due to AEs. Laboratory tests, vital signs, findings from physical examinations, and ECGs will be summarized for changes over time during treatment using descriptive statistics.

7.6.7 Other Analyses

Descriptive summaries of demographic and baseline characteristics will be presented by treatment group and overall for the placebo-controlled treatment period and by treatment assigned at randomization in the OLE.

Efficacy data will be summarized at each scheduled visit in the OLE, and subjects will be grouped according to initial treatment assigned at randomization.

Descriptive statistics will include the number of non-missing observations, mean, standard deviation, median, minimum, and maximum for quantitative data. For qualitative data, frequency counts and percentage will be determined. A full description of demographic variables will be included in the SAP(s).

Individual subject demographics and baseline information will be provided in data listings.

Medical history will be coded using MedDRA at the time of each database lock and will be summarized using the number of observations and percentages of subjects reporting each category and listed for each subject.

A list of protocol deviations (major or minor) will be finalized prior to each database lock.

